13.4.2 Analysis of Secondary Effectiveness Endpoints

The secondary effectiveness endpoints are

- monocular BCDVA at 4 m
- monocular DCNVA at 40 cm
- monocular depth of focus assessed by the mean defocus curve
- monocular mesopic contrast sensitivity at 12 cycles per degree with and without glare respectively
- proportion of subjects who respond “Never” to Q1 and Q3 of the spectacle use questionnaire respectively

13.4.2.1 Statistical Hypotheses

The null and alternative hypotheses for the first secondary analysis are:

$$H_0: \mu_{DFT015VA} - \mu_{SN60WFVA} \geq \Delta$$

$$H_A: \mu_{DFT015VA} - \mu_{SN60WFVA} < \Delta$$

where Δ refers to the non-inferiority margin, set at 0.10 logMAR, and $\mu_{DFT015VA}$ and $\mu_{SN60WFVA}$, refer to the mean monocular BCDVA at 4 m for the test and control lenses, respectively, in the first implanted eye. [REDACTED]

The null and alternative hypotheses for the second secondary analysis are:

$$H_0: \mu_{DFT015VA} \geq \mu_{SN60WFVA}$$

$$H_A: \mu_{DFT015VA} < \mu_{SN60WFVA}$$

where $\mu_{DFT015VA}$ and $\mu_{SN60WFVA}$ refer to the mean monocular photopic DCNVA at 40 cm for the test and control lenses, respectively, in the first implanted eye. [REDACTED]

The null and alternative hypotheses for the fourth secondary analysis are:

$$H_0: \mu_{DFT015CS} - \mu_{SN60WFCS} \leq \Delta$$

$$H_A: \mu_{DFT015CS} - \mu_{SN60WFCS} > \Delta$$

where Δ refers to the non-inferiority margin set at -0.15 log unit, and $\mu_{DFT015CS}$ and $\mu_{SN60WFCS}$ refer to the mean monocular mesopic contrast sensitivity score (log unit) for the test and control lenses, respectively, in the first implanted eye. [REDACTED]

The null and alternative hypotheses for the fifth secondary analysis are:

$$H_0: \pi_{DFT015} \leq \pi_{SN60WF}$$

$$H_A: \pi_{DFT015} > \pi_{SN60WF}$$

where π_{DFT015} and π_{SN60WF} refer to the proportion of subjects who responded “Never” for the test and control lenses.

13.4.2.2 Analysis Methods

The statistical model associated with the above hypotheses for the first secondary effectiveness analysis will be tested by generating a one-sided 97.5% upper confidence limit based on the difference in means (ACRYSOF IQ EDF IOL – ACRYSOF IQ Monofocal IOL) using a two-sample t-test. The upper bound of the one-sided 97.5% confidence limit will be compared to the margin, 0.10 logMAR. If the upper bound is less than the margin, the null hypothesis will be rejected and it will be concluded that ACRYSOF IQ EDF IOL is non-inferior to ACRYSOF IQ Monofocal IOL for BCDVA at 4 m.

Descriptive statistics (mean, median, SD, number of eyes, minimum, maximum and (two-sided) 95% confidence interval) will also be provided for monocular BCDVA at 4 m, separately for each eye.

For the second secondary effectiveness analysis, treatment group comparison for photopic DCNVA will be made and the objective will be demonstrated if (one-sided) $P < 0.025$ from a two-sample t-test.

Descriptive statistics (mean, median, SD, number of eyes, minimum, maximum and (two-sided) 95% confidence interval) will also be provided for monocular DCNVA at 40 cm, separately for each eye.

For the third secondary effectiveness analysis (depth of focus), the line plot of the average VA at each defocus level (ie, defocus curve) will be used to estimate the negative lens induced depth of focus at 0.20 logMAR. The difference in depth of focus between ACRYSOF IQ EDF IOL and ACRYSOF IQ Monofocal IOL will be presented.

The hypotheses for the fourth secondary effectiveness analysis will be tested by generating a one-sided 97.5% lower confidence limit based on the difference in means (ACRYSOF IQ EDF IOL – ACRYSOF IQ Monofocal IOL) using a two-sample t-test. The lower bound of the one-sided 97.5% confidence limit will be compared to the margin, -0.15 log unit. If the lower bound is greater than the margin, the null hypothesis will be rejected and it will be concluded that ACRYSOF IQ EDF IOL is non-inferior to ACRYSOF IQ Monofocal IOL for monocular mesopic contrast sensitivity. Monocular mesopic contrast sensitivity without glare at 12 cycles per degree will best tested followed by monocular mesopic contrast sensitivity with glare at 12 cycles per degree.

[figure not shown]
For the fifth secondary effectiveness endpoint, a two-sided 95% confidence interval for the difference in proportions (ACRYSOF IQ EDF IOL – ACRYSOF IQ Monofocal IOL) will be calculated using the Miettinen-Nurminen method (1985), and ACRYSOF IQ EDF IOL will be determined to be superior to ACRYSOF IQ Monofocal IOL if the lower boundary of the confidence interval is greater than zero. This is equivalent to using a type I error rate of 2.5%, 1-sided. Response to Q3 of spectacle use questionnaire will best tested followed by response to Q1 of spectacle use questionnaire.

[REDACTED]

[REDACTED]

- [REDACTED]
- [REDACTED]
- [REDACTED]
- [REDACTED]
- [REDACTED]
- [REDACTED]
- [REDACTED]
- [REDACTED]
- [REDACTED]
- [REDACTED]
- [REDACTED]
- [REDACTED]

The following primary and secondary effectiveness analyses will be performed on the Month 6/Visit 5A (120-180 day post 2nd eye implantation) data using the sequential testing approach summarized in the figure below if the primary and both secondary null hypotheses are rejected for the Month 3/Visit 4A (70-100 day post 2nd eye implantation) analysis.

13.7 Safety Analysis

Adverse Events and Device Deficiencies

Descriptive summaries (counts and percentages) for specific AEs will be presented by IOL group. The one-sided exact 95% lower confidence limit of incidence rates (proportion of eyes with events) observed for each IOL group will be compared to the cumulative and persistent adverse event SPE rates. In addition to SPE rates predefined in IS EN ISO 11979-7, the rate of adverse events that may be specifically related to ACRYSOF IQ EDF IOL design features; and any other significant events will be provided. These rates will be accompanied by two-sided exact 95% confidence intervals.

The number and percentage of all adverse events will be tabulated with a breakdown by IOL group and implanted eye. A listing of all adverse events will also be provided.

The number and percentage of all device deficiencies will be tabulated with a breakdown by IOL group and implanted eye. A listing of all device deficiencies will also be provided.

[REDACTED]

[REDACTED]

[REDACTED]

[REDACTED]

[REDACTED]

[REDACTED]

[REDACTED]

[REDACTED]

[REDACTED]

[REDACTED]

[REDACTED]

13.8 Health Economics

Not Applicable.

13.9 Interim Analyses

Not Applicable.

13.10 Non-inferiority Margin

The non-inferiority margin used for the first secondary objective analysis will be 0.10 logMAR which equals 1 line in logMAR VA. The non-inferiority margin used for the fourth secondary objective analysis will be -0.15 log unit.

13.11 Sample Size Justification

Effectiveness

The proposed sample size (N = 234; 130 Bilateral ACRYSOF IQ EDF IOL and 104 Bilateral ACRYSOF IQ Monofocal IOL) provides >99% power for the superiority hypothesis test on mean monocular DCIVA (66 cm) when tested at the 0.025 level of significance (one-sided) assuming the difference in means is -0.12 logMAR (SD = 0.18).

The proposed sample size (N = 234; 130 Bilateral ACRYSOF IQ EDF IOL and 104 Bilateral ACRYSOF IQ Monofocal IOL) provides 81% power for the non-inferiority

hypothesis with respect to mean monocular BCDVA (4 m) when tested at the 0.025 level of significance (one-sided) with a non-inferiority margin of 0.10 logMAR assuming the difference in means is 0.04 logMAR (SD = 0.16).

The proposed sample size (N = 234; 130 Bilateral ACRYSOF IQ EDF IOL and 104 Bilateral ACRYSOF IQ Monofocal IOL) provides >99% power for the superiority hypothesis test on mean monocular DCNVA (40 cm) when tested at the 0.025 level of significance (one-sided) assuming the difference in means is -0.12 logMAR (SD = 0.18).

The proposed sample size (N = 234; 130 Bilateral ACRYSOF IQ EDF IOL and 104 Bilateral ACRYSOF IQ Monofocal IOL) provides 74% power for the non-inferiority hypothesis with respect to mean monocular mesopic contrast sensitivity value when tested at the 0.025 level of significance (one-sided) with a non-inferiority margin of -0.15 log unit assuming the difference in mean is -0.02 log unit (SD = 0.38).

The expected sample size (N = 131) will provide 84% power, with $\alpha=0.025$, 1-sided, to detect a difference of 25% in proportion of subjects who respond “Never” to Q1 and Q3 of the spectacles use questionnaire respectively, assuming a 50% rate in the ACRYSOF IQ EDF IOL group.

Approximately 260 subjects will be randomized to achieve 234 subjects who complete the study. It is expected that approximately 131 subjects will respond to spectacle use questionnaire in this study.

Adverse Events

For any event where zero incidences is observed in 130 operative eyes with ACRYSOF IQ EDF IOL, the upper limit of the 95% 1-sided exact binomial confidence interval is less than 2.3%. Thus, with 95% confidence the true adverse event rate is less than 2.3%.

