13.4 Effectiveness Analyses

A total of three hypothesis tests will be conducted to address the primary and secondary effectiveness objectives of the study. Overall Type I error will be maintained at the 0.05 level using a sequential testing approach.

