4.4 Multiplicity Strategy

Overall type I error will be maintained at 0.05 level for the Month 3/Visit 4A (70-100 day post 2nd eye implantation) analyses using the sequential testing approach summarized in the figure below.

The following primary and secondary effectiveness analyses will be performed on the Month 6/Visit 5A (120-180 day post 2nd eye implantation) data using the sequential testing approach summarized in the figure below if the primary and both secondary null hypotheses are rejected for the Month 3/Visit 4A (70-100 day post 2nd eye implantation) analysis. If any null hypothesis is not rejected, no further hypothesis testing will be performed.

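### The power stated for the Month 6 secondary tests is per-test power and leaves out the Month 3 gate, which caps every Month 6 claim at about 81% at the planned 234 subjects

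*Protocol*

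**What the plan says.** Protocol 3, Protocol 13.11 and SAP 7 give one power figure per endpoint, each at one-sided 0.025. In Protocol 13.11:

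- BCDVA at 4 m: the sample "provides 81% power for the non-inferiority" test.
- DCNVA: it "provides >99% power for the superiority hypothesis test on mean monocular DCNVA (40 cm"); the DCIVA figure is also above 99%.
- Contrast sensitivity: it "provides 74% power for the non-inferiority hypothesis with respect to mean monocular mesopic contrast sensitivity value".
- Spectacle use, items Q1 and Q3: "The expected sample size (N = 131) will provide 84% power".

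SAP 7 repeats these from the same inputs, except that it gives 74% for BCDVA.

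The testing rule is in SAP 4.4. Month 6 tests are done "if the primary and both secondary null hypotheses are rejected" at Month 3, and "If any null hypothesis is not rejected, no further hypothesis testing will be performed". Protocol 3 and the multiplicity text of Protocol 13 state the same gate. The two Month 3 secondaries with hypotheses are BCDVA and DCNVA; SAP 4.2.2 says that the defocus objective has none.

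Within Month 6 the text fixes two partial orders. For contrast sensitivity, "Monocular mesopic contrast sensitivity without glare at 12 cycles per degree will best tested followed by monocular mesopic contrast sensitivity with glare" (Protocol 13.4.2.2); for spectacle use, Q3 comes before Q1. The order between the two pairs is in a figure that is not shown. Protocol 13.4 says: "A total of three hypothesis tests will be conducted".

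**The concern.** A power figure beside a confirmatory objective is normally read as the chance of making that claim if the assumptions hold. Here a Month 6 claim needs DCIVA, BCDVA and DCNVA all to succeed first, then every earlier step at Month 6. None of the three power sections mentions this. Two chained contrast tests share one 74%, and two chained spectacle items share one 84%.

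The stake is planning. A reader of 13.11 would expect roughly a three-in-four chance of the contrast claim and five-in-six for spectacle use. On the plan's own inputs, about one trial in five misses BCDVA and never formally tests either.

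**Working it through.** **Inputs (Protocol 13.11, SAP 7).** n = 130 and 104, one-sided alpha 0.025. DCIVA and DCNVA: difference -0.12, SD 0.18. BCDVA: difference 0.04, SD 0.16, margin 0.10, so 0.06 from the margin. Contrast sensitivity: difference -0.02, SD 0.38, margin -0.15, so 0.13 from the margin. Spectacle use: 50% against 25%, N = 131. The 5:4 split to 73 and 58 is my assumption.

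**Step 1: reproduce the stand-alone figures.** Power is the probability that a noncentral t with 232 df exceeds its critical value. The noncentrality is distance / (SD × √(1/130 + 1/104)), and the root is 0.1316.

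- DCIVA, DCNVA: 0.12 / (0.18 × 0.1316) = 5.07, power 0.999.
- BCDVA: 0.06 / (0.16 × 0.1316) = 2.85, power 0.810 (normal approximation 0.813). This matches the Protocol's 81%, not the SAP's 74%.
- Contrast sensitivity: 0.13 / (0.38 × 0.1316) = 2.60, power 0.736 (normal 0.739). Stated 74%.
- Spectacle use: pooled rate (36.5 + 14.5)/131 = 0.389, pooled SE 0.0858, unpooled SE 0.0816. Then Φ[(0.25 - 1.96 × 0.0858)/0.0816] = Φ(1.00) = 0.842. The exact power of the Miettinen-Nurminen test is also 0.842. Stated 84%.

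**Step 2: the cap.** A Month 6 rejection requires the BCDVA rejection, so for any order and any correlation

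P(Month 6 claim) ≤ min(0.810, power of that test).

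This gives 0.810 for spectacle use, below the stated 0.84. For contrast sensitivity it gives 0.736, the stated 74% itself.

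**Step 3: independence.** Gate = 0.999 × 0.810 × 0.999 = 0.809. Multiplying along the chain:

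| Claim | Contrast pair first | Spectacle pair first |
|---|---|---|
| Contrast, without glare | 0.809 × 0.736 = 0.59 | 0.574 × 0.736 = 0.42 |
| Contrast, both conditions | 0.595 × 0.736 = 0.44 | 0.422 × 0.736 = 0.31 |
| Q3 | 0.437 × 0.842 = 0.37 | 0.809 × 0.842 = 0.68 |
| Q3 and Q1 | 0.368 × 0.842 = 0.31 | 0.681 × 0.842 = 0.57 |

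**Step 4: correlation.** The plan gives none. With one common correlation among all test statistics (simulated normal model):

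| Correlation | Q3 first | Contrast without glare first | Both contrast, tested first | Q3 after both contrast |
|---|---|---|---|---|
| 0.3 | 0.70 | 0.62 | 0.50 | 0.46 |
| 0.5 | 0.72 | 0.65 | 0.55 | 0.52 |
| 0.9 | 0.78 | 0.71 | 0.67 | 0.66 |

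**Step 5: more subjects at Month 3.** Protocol 9 defines the 234 as completers of Visit 5A, so more could contribute at Month 3. BCDVA power is 0.842 at N = 255 and 0.849 at N = 260. Multiplying by 0.842 gives 0.71 and 0.72 for Q3 tested first under independence.

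**Step 6: the SAP's own BCDVA figure.** At face value, 74% would cap all Month 6 claims at 74%, with products 0.74 × 0.84 = 0.62 and 0.74 × 0.74 = 0.55.

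**The case against.** The strongest reply is that nothing is miscalculated. The Protocol's figures all reproduce, and they are worded as power at a stated one-sided level, not as the chance of a claim after the sequence. SAP 4.4 states the stopping rule openly, and the 81% stands in the same section as the other figures. That stands: this is missing labelling and missing sequential power, not an arithmetic error. The exception is the SAP's 74% for BCDVA.

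Two stronger readings should be set aside. A reader might infer that 84% is impossible whatever happens. The documents do not support that: the 81% cap belongs to N = 234, and if all 260 randomised subjects gave Month 3 data it would be about 85%. Even then, 84% would need near-perfect dependence between the tests. A reader might also infer that 74% for contrast sensitivity is excluded. It equals the upper bound, so it is optimistic but not excluded.

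It is also fair that the Month 6 order cannot be seen. The rule speaks of primary and secondary analyses on Month 6 data, so the figure may repeat acuity tests there. Hence no single replacement value can be prescribed, and the three tests in Protocol 13.4 cannot simply be changed to seven. Three may mean the Month 3 family alone.

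Finally, the SAP's executive summary makes study success depend at least on the primary objective, which the gate does not touch. That limits the consequence; it does not make the Month 6 figures describe the design.

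**Conclusion.** The point holds as one of labelling and completeness. The stand-alone figures are correct, apart from the BCDVA power in SAP 7, but they overstate the chance of a formal Month 6 claim. At the planned 234, the cap is about 81%, so the 84% for spectacle use is not attainable as a claim probability, and the 74% for contrast sensitivity is a ceiling. Under independence, Q3 lies at 68% or 37% and contrast sensitivity without glare at 59% or 42%, depending on which pair comes first; positive correlation raises these. The values rest on the plan's effect sizes and SDs, the assumed 5:4 split of the 131 responders, and no further Month 6 test ahead of these. Any such test would lower them. If DCNVA follows BCDVA at Month 3, its figure of over 99% likewise becomes about 81%; that order is also in a figure not shown. Type I error control and the primary objective's power are unaffected.

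**What to change.** In Protocol 3, Protocol 13.11 and SAP 7:

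1. Label the current figures as per-test power, if tested alone.
2. Beside each, give the power to reach and reject that step, using the actual order in the multiplicity figures and a stated correlation, with independence as a reference case.
3. Give contrast sensitivity without and with glare separately, and Q3 and Q1 separately.
4. Correct the BCDVA power in SAP 7 from 74% to 81%, as its inputs imply.
5. In Protocol 13.4, make the count of three tests agree with the sequence figures, or say that it covers Month 3 only.

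This costs wording and a short calculation; no patients, tests or alpha are added. The drawback is that the published Month 6 figures become less favourable.

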14 DATA HANDLING AND ADMINISTRATIVE REQUIREMENTS

14.1 Subject Confidentiality

The Investigator must ensure that the subject’s anonymity is maintained throughout the course of the study. In particular, the Investigator must keep an enrollment log with confidential identifying information that corresponds to the subject numbers and initials of each study participant. At the end of the clinical study, the Study Sponsor will collect a copy of the enrollment log **without any identifying subject information**. All documents

submitted to the Study Sponsor will identify the subjects exclusively by number and demographic information. No other personally identifying information will be transmitted to the Study Sponsor.

The Study Sponsor may release anonymized study data to external researchers for purposes of future research directly related to the study objectives, or future research that is beyond the scope of the current study objectives. The ICF explains this to study subjects. Anonymization means that all identifiable information will be removed from the dataset and all links to the subjects in the study will be removed. Anonymization of the data will maintain confidentiality of the subjects who participate in the study so that they cannot be identified by external researchers. The anonymized data set will contain records from all of the subjects in the current study, but the anonymization process might change the data set in some ways, so external researchers will be informed that they might not be able to duplicate some of the results from this study.

External researchers who request permission to use anonymized data from studies for a new medicine or new indication of a medicine (studies for approved medicinal products, small molecule generics, and devices are excluded) must be approved by a central independent review panel that will adjudicate the scientific request and the competency of the external researcher(s), as well as determine the applicability to current standard operating procedures (SOPs). If approved, a data sharing agreement will be executed between the Study Sponsor and the external researcher(s), committing to a specified analysis and publication timeline. Anonymized data will be released to external researchers only after European Union (EU) and/or United States (US) submission of the investigational drug/biologic for the study indication. The Study Sponsor will not be able to influence the analyses that are performed by external researchers using the data from this study once the anonymized data are released.

14.2 Completion of Source Documents and Case Report Forms

The nature and location of all source documents will be identified to ensure that original data required to complete the eCRFs exist and are accessible for verification by the site monitor, and all discrepancies must be appropriately documented via the query resolution process. Study monitors are appointed by the Study Sponsor and are independent of study site staff.

If electronic records are maintained, the method of verification must be determined in advance of starting the study. At a minimum, source documents include the following information for each subject:

- Subject identification (name, sex, race/ethnicity)
- Documentation of subject eligibility
- Date of informed consent
- Dates of visits
- Documentation that protocol specific procedures were performed
- Results of study parameters, as required by the protocol
- IP accountability records
- Documentation of AEs and other safety parameters (if applicable)
- Records regarding medical histories and the use of concomitant therapies prior to and during the study
- Date of study completion and reason for early discontinuation, if applicable

It is required that the author of an entry in the source documents be identifiable. Direct access to source documentation (medical records) must be allowed for the purpose of verifying that the data recorded on the eCRF are consistent with the original source data.

Only designated individuals at the site will complete the eCRFs. The eCRFs must be completed at regular intervals following the clinical study visit schedule. It is expected that all data reported have corresponding entries in the source documents. The Investigator is responsible for reviewing and certifying that the eCRFs are accurate and complete. The only subject identifiers recorded on the eCRFs will be subject number, and subject demographic information.

14.3 Data Review and Clarifications

A targeted review of eCRF data to the subject's source data will be completed by the site monitor to ensure completeness and accuracy. After the eCRFs have been completed, additional data clarifications and/or additions may be needed as a result of the data cleaning process. Data clarifications are documented and are part of each subject's eCRF.

14.4 Sponsor and Monitoring Responsibilities

The Study Sponsor will designate a monitor to conduct the appropriate site visits at the appropriate intervals. The clinical investigation will be monitored to ensure that the rights and well-being of the subjects are protected, the reported data are accurate, complete, and verifiable from the source documents, and the study is conducted in compliance with the current approved protocol (and amendments[s], if applicable), with current GCP, and with applicable regulatory requirements.

All sites must have a site initiation. Prior to screening subjects or performing the informed consent process on any subject, the site must receive a Site Activation Notification from an appropriate Study Sponsor representative. Monitoring will be conducted periodically while the clinical study is ongoing. Monitoring methods may include site visits, telephone, written and fax correspondence. Close-out visits will take place after the last visit of the last subject or after database lock.

A Coordinating Investigator (CI) may be identified by the Study Sponsor. In cases where a CI is required, the Study Sponsor will select the CI based upon their experience, qualifications, active study participation, and their willingness and availability to take on this role. The CI will be bound by confidentiality obligations described in a separate confidentiality agreement between the CI and the Study Sponsor.

